### **6.9.4 Vital Signs and Body Weight**

Descriptive statistics of vital sign (systolic blood pressure, diastolic blood pressure, heart rate, body weight) data at each post randomization time point (both absolute and change) will be presented by final dose group and treatment group (i.e., octreotide 40, 60, 80, overall and placebo). Summaries will be provided for the DPC period and for the OLE period. In calculating the change from baseline for both the DPC and for the OLE, the baseline for the DPC period will be used.

Additionally, shift tables, summarizing individual subject changes from baseline to end of treatment will be presented for heart rate, diastolic and systolic blood pressure, by final dose group and treatment group (i.e., octreotide 40, 60, 80, overall and placebo), using the categories outlined in the common terminology criteria for adverse events (CTCAE) version 4.03.

These will be presented for both the DPC period and OLE period. For both the DPC period and the OLE period, shifts from baseline will use the baseline defined for the start of the DPC period.

Subjects with clinically significant abnormalities will be identified in listings.

All tabular summaries will exclude any data that was collected after a subject had discontinued study drug. Data collected after a subject had discontinued study drug will be included in listings.

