|  | 
[REDACTED]
 
The duration of the DPC period for each patient will be 36 weeks. The octreotide capsule dose/placebo should be titrated up per Investigator's discretion, based on significantly increased IGF-1 levels compared to Baseline (average of the 2 assessments within 2 weeks prior to randomization), worsening of acromegaly signs/symptoms or both.
 
The Sponsor recommends any one of the following guiding rules for dose escalation:
 
 
• Significantly increased IGF-1 levels compared to Baseline defined as IGF-1 increase by at least 30% to <math>>1 \times \text{ULN}</math> (this will be flagged by the central laboratory).
 
• IGF-1 levels <math>>1 \times \text{ULN}</math> for 2 consecutive visits.
 
• New or worsening of any one of the following acromegaly signs/symptoms: headache, fatigue, perspiration, soft tissue swelling, arthralgia, dysglycemia or hypertension or other signs that in view of the Investigator are related to acromegaly.
 
 
The dose escalation will be done in a stepwise manner from 1 capsule twice daily; BID (equivalent to 40 mg/day) to 2 capsules in the morning and 1 capsule in the evening/night (equivalent to 60 mg/day) to 2 capsules BID (equivalent to 80 mg/day).
 
The dose can be escalated any time through Week 24 (including Week 24); thereafter the dose must be kept stable. Patients randomized to matching placebo will also undergo mock titrations increasing capsule numbers from 1 capsule twice daily to 2 capsules in the morning and 1 capsule in the evening/night to 2 capsules BID.
 
During the DPC period, patients will return to the clinic for a site visit every four weeks up to week 36 (<math>\pm 5</math> days) and attend an additional in-clinic visit at week 34 (<math>\pm 5</math> days).
 
[REDACTED] Pre-scheduled telephone calls will occur at Weeks 1 and 2. Unscheduled visits will be allowed throughout the study for safety, tolerability or management of active disease, per the Investigator discretion.
 
[REDACTED]
 
All efforts should be made to maintain patients on their randomized arm assignment throughout the DPC period up to completion of the core study.
 
Patients who meet the pre-defined withdrawal criteria [(IGF-1 levels <math>\geq 1.3 \times \text{ULN}</math> AND exacerbation of acromegaly clinical signs or symptoms), for 2 consecutive
 |
|--|---|

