## 5.2 DOUBLE-BLIND PLACEBO-CONTROLLED (DPC) PERIOD (WEEK 1 TO WEEK 36)

Patients meeting the eligibility criteria will be randomized at Baseline in 1:1 ratio to one of two treatment arms: Octreotide capsules or matching placebo capsules. All efforts should be made to

---

 Including assay used and/or reference ranges

maintain patients on their randomized arm assignment throughout the DPC period up to completion of the core study.

The octreotide capsule dose/placebo should be titrated up per Investigator's discretion, based on significantly increased IGF-1 levels compared to Baseline (average of the 2 assessments within 2 weeks prior to randomization), worsening of acromegaly signs/symptoms or both (see Section 6.2).

During the DPC period, patients will return to the clinic for a site visit every four weeks ( $\pm 5$  days) up to week 36 and attend an additional in-clinic visit at week 34 to collect 2 consecutive assessments [REDACTED]. Patients who miss week 34 visit will be scheduled to attend an unscheduled visit.

Pre-scheduled telephone calls will occur at weeks 1 and 2. Unscheduled visits will be allowed throughout the study for safety, tolerability or management of active disease, per the Investigator discretion. If  $\text{IGF-1} \geq 1.3 \times \text{ULN}$  at any visit, or upon physician assessment of exacerbation of clinical symptoms, the patient should be invited to an unscheduled visit within two weeks of the first assessment.

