### 6.2 STUDY MEDICATION ADMINISTRATION

Study medication should be administered twice daily with a glass of water (240 mL) on an empty stomach, i.e. at least one hour prior to a meal or at least two hours after a meal.

Optional/recommended drug administration timing to patients:

Morning Dose

- Take the morning dose first thing in the morning and have breakfast at least one hour later OR
- Have breakfast and take the morning dose at least two hours later and at least one hour prior to lunch

Evening Dose

- Take the evening dose before going to bed, at least two hours after dinner or any other snack OR
- Take your evening dose at least 1 hour prior to dinner and at least two hours following an earlier snack/meal

During DPC period, study medication will be up-titrated up in all eligible patients from 1 capsule twice daily; BID (equivalent to 40 mg/day) to 2 capsules in the morning and 1 capsule in the evening/night (equivalent to 60 mg/day) to 2 capsules BID (equivalent to 80 mg/day).

The dose can be escalated any time through week 24 (including week 24); thereafter the dose must be kept stable.

The Sponsor recommends the following guiding rules for dose escalation:

- Significantly increased IGF-1 levels compared to Baseline defined as IGF-1 increase by at least 30% to  $>1 \times \text{ULN}$  (this will be flagged by the central laboratory)
- IGF-1 levels  $>1 \times \text{ULN}$  for 2 consecutive visits
- New or worsening of any one of the following acromegaly signs/symptoms: headache, fatigue, perspiration, soft tissue swelling, arthralgia, dysglycemia or hypertension or other signs that in view of the Investigator are related to acromegaly.

During the OLE period, the initial octreotide capsules dose will be 60 mg for all patients. The dose can be escalated or de-escalated upon the investigator's discretion, based on either IGF-1 and/or safety and tolerability.

The Sponsor recommends the following guiding rules for dose de-escalation:

- IGF-1 decreased by at least 50% on two consecutive visits, compared to baseline (average of 2 assessments within 2 weeks prior to randomization) and acromegaly signs/symptoms are adequately controlled (as determined by study investigator). OR

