### 6.9.1 Study Drug Exposure and Compliance

#### 6.9.1.1 DPC period

Octreotide capsules can be up-titrated during the DPC period from 40 mg/day to 60 mg/day and 60 mg/day to 80 mg/day, based on clinical and biochemical response.

In the DPC period, the duration of study drug exposure (in days) will be summarized by the treatment group and overall, using descriptive statistics. Duration of study drug exposure will be calculated as date of last dose in the DPC period – date of first dose in the DPC period + 1.

Descriptive statistics for the time to the first dose escalation from 40 mg to 60 mg and time to the second dose escalation from 60 mg to 80 mg will also be presented by treatment group. A figure depicting the time to each dose escalation for each patient will be presented

The number and proportion of patients at each dose level (40, 60 and 80 mg/day) at the end of the DPC period, will also be presented by treatment group.

Compliance to each dose level of octreotide capsules from first dose in the DPC period through the last visit of the DPC period will be calculated and summarized by treatment group overall, and also by the final target dose level achieved within each treatment group.

For the purpose of analysis, compliance to each dose level during the DPC period will be calculated as  $100 \times (\text{total number of capsules actually taken} / \text{total number of capsules expected to be taken})$ . This calculation will be used for each dose level the patient received during the DPC period. The numbers and percentages of patients <75% compliant, 75-100% compliant, and >100% compliant will be tabulated.

The number of actual capsules taken for each dose level will be the total number of capsules dispensed – total number of capsules returned during the time the patient was on that particular dose.

The number of expected capsules taken for the target dose level will be derived as follows:

Dose Level	Expected Number of Capsules Taken
40 mg	2 capsules $\times$ (first day of the phase – last day of the phase)
60 mg	3 capsules $\times$ (first day of the phase – last day of the phase)
80 mg	4 capsules $\times$ (first day of the phase – last day of the phase)
Overall	Sum of expected number of capsules taken over all of the dose levels assigned

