### 6.9.2.1 DPC period

All AEs that occur after randomization (i.e., date of onset is on or after the date of randomization) and on or before the end of treatment (last dose of blinded study drug) in the DPC period will be considered Treatment Emergent Adverse Events (TEAEs) for the purpose of reporting in the DPC period, and will be summarized using frequency counts and percentages. Summaries will be presented by final dose group and treatment group (i.e., octreotide 40, 60, 80, overall and placebo) and overall for the safety set.

If the day of onset of an AE is missing, then if the month and year of an onset date are on or after the date of randomization, the following rules will be applied:

- If month/year of the onset date is on or after the month/year of randomization, the AE will be considered treatment emergent;
- If month/year of the onset date is equal to the month/year of randomization, and the end date is present, the end date will be used to determine when the AE started. If the end date is on or after randomization, the AE will be considered treatment emergent; otherwise, if the AE stopped before randomization, then it will not be considered treatment emergent;
- If month/year of the onset date is equal to the month/year of randomization, and the end date is a partial date, the AE will be considered treatment emergent;
- If, despite implementing the above conventions, the onset date of the AE cannot be placed before, on, or after randomization, then the event will be considered treatment emergent.

Summaries of TEAEs will be presented using the MedDRA level hierarchy (system organ class, high level group term, high level term, and preferred term) as follows:

- Overall (i.e., regardless of intensity or relationship to treatment)
- By intensity grade (mild, moderate, severe)
- By relationship to study medication (potential relationship to study treatment or unlikely/no relationship to study treatment) according to the mapping scheme below:
  - Related: will include all AEs with a relationship rating of “related” or “possibly related”
  - Not related: will include all AEs with a relationship rating of “Not related”
- Unless otherwise specified, at each level of patient summarization in reporting the incidence of the AEs, a subject will be counted once if the subject reported one or more events. If more than one occurrence of an event is reported, the event of the worst intensity or the worst-case relationship assessment will be summarized.

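### SAP safety tables split octreotide by final dose but pool placebo, so titration driven by the tabulated signs is likely to produce a dose gradient with no drug effect

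*SAP*

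**What the plan says.** **Columns.** SAP 6.9.2.1 says of DPC TEAEs: "Summaries will be presented by final dose group and treatment group (i.e., octreotide 40, 60, 80, overall and placebo) and overall for the safety set". SAP 6.9.4 gives vital signs, including the CTCAE blood pressure shift tables, "by final dose group and treatment group (i.e., octreotide 40, 60, 80, overall and placebo". SAP 6.9.3 uses the same columns for by-visit chemistry, which includes glucose. SAP 6.9.5 and 6.9.6 use them for ECG and ultrasound.

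**How final dose is reached.** Protocol 5.2 sets one rule for both arms: "The octreotide capsule dose/placebo should be titrated up per" the investigator's discretion. The recommended triggers in Protocol 6.2 are IGF-1 rises (one of them required "for 2 consecutive visits") and "New or worsening of any one of the following acromegaly signs/symptoms: headache, fatigue, perspiration, soft tissue swelling, arthralgia, dysglycemia or hypertension". On timing, the same section says: "The dose can be escalated any time through week 24 (including week 24); thereafter the dose must be kept stable". The DPC rules describe upward steps only.

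**Placebo.** From the Synopsis: "Patients randomized to matching placebo will also undergo mock titrations increasing capsule numbers from 1 capsule twice daily", then to three and four capsules a day. SAP 6.9.1.1 already reports compliance "also by the final target dose level achieved within each treatment group" and end-of-period dose level by treatment group, so the mock level is available for placebo patients.

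**Overlap with outcomes.** The seven signs named as triggers are the AESIs in Protocol 7.1.1 and SAP 6.9.2.1. Protocol 7.1.1 defines worsening hypertension as a CTCAE grade shift, which is also what SAP 6.9.4 tabulates.

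**The concern.** Final dose is partly a record of what happened to the patient. Someone whose blood pressure or symptoms worsen tends to be moved up. Someone left on 40 mg tends to be a patient in whom nothing happened. Tabulating those signs by final dose sorts patients by outcome and then labels the groups with doses. An event on 40 mg that prompts escalation is shown under 60 or 80 mg.

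The same sorting happens among placebo patients, but a single placebo column hides it. A reader then sees octreotide 40 looking better than placebo and octreotide 80 looking worse, and may take this for dose-related harm. The table that would show a gradient arising without active drug is not planned, although the data for it exist. By-visit blood pressure and glucose cannot be repaired by re-dating events to the dose at onset, because there is no event to re-date.

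**Working it through.** The plan states no figure on this point, and the documents give no AESI or escalation rates. Every rate below is an assumption.

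**1. AESI incidence by final level, no drug effect on AESIs**

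From the documents: ten DPC clinic visits (Protocol 5.2.3), six of them up to week 24, when escalation is allowed; one-step moves from 2 to 3 to 4 capsules.

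Assumed:
- AESI probability of 5% per visit in both arms, independent between visits
- IGF-1-driven escalation *r* per titration visit of 8% on octreotide and 20% on placebo
- a share *q* of AESIs that lead to escalation, either 1 or 0.5

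Formulae:
- Overall incidence in either arm = 1 − 0.95^10 = 1 − 0.5987 = 40.1%.
- Escalation probability per titration visit: p = 1 − (1 − 0.05q)(1 − r).
- With x the per-visit probability, the chances of ending at 2, 3 or 4 capsules are B0(x) = (1 − x)^6, B1(x) = 6x(1 − x)^5 and B2(x) = 1 − B0 − B1.
- A patient with no AESI at any visit (probability 0.5987) escalates only through IGF-1, so AESI incidence at level k = 1 − 0.5987 × Bk(r)/Bk(p).

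Octreotide, q = 1: p = 1 − 0.95 × 0.92 = 0.126
- 40 mg: 1 − 0.5987 × 0.6064/0.4457 = 18.5%
- 60 mg: 1 − 0.5987 × 0.3164/0.3855 = 50.9%
- 80 mg: 1 − 0.5987 × 0.0773/0.1687 = 72.6%

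The other rows use the same formula:

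| Arm | q | p | 2 caps (40 mg) | 3 caps (60 mg) | 4 caps (80 mg) | Arm total |
|---|---|---|---|---|---|---|
| Octreotide | 1 | 0.126 | 18.5% | 50.9% | 72.6% | 40.1% |
| Placebo, split | 1 | 0.240 | 18.5% | 35.5% | 53.3% | 40.1% |
| Octreotide | 0.5 | 0.103 | 30.3% | 47.2% | 61.5% | 40.1% |
| Placebo, split | 0.5 | 0.220 | 30.3% | 38.2% | 47.6% | 40.1% |

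Against pooled placebo, octreotide 80 shows a spurious excess of about 32 points (q = 1) or 21 points (q = 0.5). Splitting placebo reveals a gradient there too. It does not equalize matching levels: at four capsules 72.6% faces 53.3%, and with q = 0.5, 61.5% faces 47.6%.

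**2. Wider range**

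A simulation of one million patients per arm let risk vary between patients (log-normal SD 0.7), with AESI rates of 5–15% per four weeks, 50–90% of AESIs leading to escalation, and IGF-1 escalation per four weeks of 3–10% on octreotide and 25% on placebo. Octreotide 40 ran from 17 to 56% and octreotide 80 from 61 to 99%. The arm totals agreed in every run (40 v 40, 61 v 61, 74 v 74%). In a 25-patient arm (10% AESI, 50% escalation, 5% IGF-1 escalation), the 80 column exceeded the 40 column in about 95% of the simulated trials that had patients in both.

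**3. Systolic pressure at week 36, no drug effect**

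Assumed: drift SD 4 mmHg per visit, measurement SD 6, trigger at a rise above 12 mmHg, half of triggers acted on, and IGF-1 escalation of 5% on octreotide and 25% on placebo.
- Octreotide 40/60/80: −2.6/+0.4/+6.1 mmHg
- Placebo by mock level: −2.6/−1.5/+1.2 mmHg
- Both arm totals: 0.0

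Glucose was not simulated. The argument there rests on dysglycemia being a listed trigger.

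**4. GI events with early stopping**

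Assumed: GI events in 10% or 20% of patients per four weeks over the first eight weeks, half of them stopping drug. Incidence at 40/60/80 mg is 24/14/11% or 43/28/22%, so the gradient reverses.

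**The case against.** The strongest reply is that the randomized comparison is already in the tables. Each column list includes octreotide overall beside placebo, and that contrast is free of the selection described here. SAP 6.9 plans no safety hypothesis tests. Serious TEAEs, TEAEs leading to discontinuation and the general laboratory shift tables are by treatment group. All of this stands. A reader might infer that the planned safety comparison with placebo is itself biased; it is not biased by this mechanism.

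Other limits also stand:
- Escalation is discretionary and the triggers are recommendations. Protocol 6.10.3 lets symptoms be treated medically while the patient stays in the study. A false gradient is therefore likely, not certain, and its size depends on unknown rates.
- Protocol 7.6 says patients with severe or persistent GI symptoms should be discontinued, which can leave them at a low final dose and reverse the gradient.
- ECG, ultrasound, heart rate and weight are not listed triggers. The mechanism is not shown for them, though their tables use the same columns.
- The AESI paragraph in SAP 6.9.2.1 names no dose columns. AESI terms reach the final-dose layout through the TEAE tables; a composite AESI table by dose is an inference. SAP 6.9.3 does not state the columns of the extra glucose shift table.

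A further tempting reading is that placebo at four mock capsules is a like-for-like control for octreotide 80. It is not. If octreotide holds IGF-1 down, as the primary hypothesis supposes, placebo patients reach four capsules more often through IGF-1 and are a less symptom-selected group.

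What does not stand is that descriptive tables need no guard. Dose columns beside a control invite a dose reading, Protocol 7.6 itself reports a lack of dose relationship for GI events in an earlier study, and SAP 6.9 carries no caution.

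**Conclusion.** The point holds for DPC TEAEs (including AESI terms), blood pressure and by-visit glucose. In these tables final dose is partly determined by the outcome tabulated, and the pooled placebo column conceals that the same sorting occurs without active drug. Under the assumed rates, a true 40.1% in both arms is displayed as 18.5/50.9/72.6% or 30.3/47.2/61.5% across octreotide 40/60/80. The direction is the same at every AESI rate tried. The magnitude is illustrative only.

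The documents do not support a claim that a false toxicity gradient must appear, that it always points upward, or that every safety table is affected. This is a matter of presentation and interpretation in the safety section. It does not touch the primary analysis, the type I error or the sample size, and the change is worth making because the needed data are already held.

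**What to change.** In the DPC tables of TEAEs and AESIs (SAP 6.9.2.1), glucose (6.9.3) and blood pressure (6.9.4):

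1. Show placebo by final mock level (2, 3 or 4 capsules a day) beside octreotide 40, 60 and 80, and keep both arm totals.
2. Name octreotide overall versus placebo as the safety comparison.
3. Add a statement such as: *Final dose is determined after randomization and partly by the outcomes tabulated. Final-dose columns do not support a dose-toxicity inference. Matching capsule levels are not a like-for-like comparison between arms, because placebo patients are expected to reach higher levels more often through IGF-1. Placebo is split only to show the gradient that selection produces.*

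The cost is programming and wider tables; no new data are needed. Cells will be small. With about 25 patients per arm and the q = 1 rates above, expected numbers (25 × Bk(p)) are 11.1/9.6/4.2 on octreotide and 4.8/9.1/11.1 on placebo. The octreotide dose columns already have this weakness.

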### 6.9.5 ECG

All 12-Lead ECGs will be read by a central lab. 12-Lead ECG parameters will be summarized at each time point using descriptive statistics by final dose group and treatment group (i.e., octreotide 40, 60, 80, overall and placebo). Both absolute and change from baseline will be provided for each continuous 12-Lead ECG parameter. Summaries will be provided for the DPC period and for the OLE period. In calculating the change from baseline for both the DPC and for the OLE, the baseline for the DPC period will be used.

Additionally, the numbers and percentages of patients with ECG abnormalities (as determined by the central laboratory) at each visit will be presented for both the DPC and for the OLE. The parameters and abnormality criteria are specified in the table below:

Parameter	Abnormality Criterion
PR interval	<110 ms
	>300 ms
QRS interval	$\geq$ 120 ms
QTcF	<350 ms
	Male >450 ms or Female >470 ms
	>500 ms
Heart rate	<50 bpm
	>110 bpm

Shift tables will be used to show the changes from baseline to each post baseline time point based on the above abnormality criteria for both the DPC and for the OLE periods. For both the DPC period and the OLE period, shifts from baseline will use the baseline defined for the start of the DPC period.

A listing of patients with clinically significant ECG abnormalities (using the high and low cut points above) will be provided in listings.

All tabular summaries will exclude any data that was collected after a subject had discontinued study drug. Data collected after a subject had discontinued study drug will be included in listings.

### 6.9.6 Abdominal Ultrasound

The following information will be summarized at baseline and end of treatment for the DPC period using shift tables, by final dose group and treatment group (i.e., octreotide 40, 60, 80, overall and placebo):

- Ultrasound Normality (Normal=Yes reported on eCRF; Abnormal = No)
- Biliary Sludge (Normal=No reported on eCRF; Abnormal =Yes)
- Wall Thickening (Normal=No reported on eCRF; Abnormal =Yes)
- Dilatation of Common Bile Duct (Normal=No reported on eCRF; Abnormal =Yes)

For the OLE period, shift tables will also be provided to show shifts from baseline of the DPC period to each assessment in the OLE period.

All tabular summaries will exclude any data that was collected after a subject had discontinued study drug. Data collected after a subject had discontinued study drug will be included in listings.

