### 4.2 EXCLUSION CRITERIA

Any of the following will exclude a patient from participating in the study:

1. Patients taking injections of long-acting SRLs off label (unlabeled doses or dosing interval. e.g. 60 or 90 mg lanreotide every 8 weeks or 30 mg octreotide every 6 or 8 weeks).
2. Patients who previously participated in CH-ACM-01 or OOC-ACM-302 (MPOWERED).
3. Symptomatic cholelithiasis.
4. Conventional or stereotactic Radiotherapy any time in the past.
5. Undergone pituitary surgery within six months prior to screening or have elective pituitary surgery (or other elective surgery that may affect compliance with protocol or confound study outcomes), planned within the course of the core study.

---

 Abstinence is defined as refraining from heterosexual intercourse during the screening, treatment phase and at least 2 weeks following treatment discontinuation.

6. High-risk pattern of pituitary tumor location on pituitary magnetic resonance imaging (MRI)/Computed tomography (CT) as per medical history or most recent MRI/CT.
7. History of unstable angina or acute myocardial infarction within the 12 weeks preceding the screening visit or other clinically significant cardiac disease at the time of screening as judged by the Principal Investigator.
8. Any clinically significant uncontrolled nervous system, gastrointestinal (GI), renal, pulmonary, or hepatic concomitant disease that in the Investigator's opinion would preclude patient participation.
9. Evidence of active malignant disease or malignancies diagnosed within the previous one year (except for basal cell carcinoma and uncomplicated – up to stage 1 squamous cell carcinoma that has been excised and cured).
10. Known allergy or hypersensitivity to any of the test compounds or materials.
11. Known uncontrolled diabetes defined as having a fasting glucose > 150 mg/dL (8.3 mmol/L) or glycosylated hemoglobin (HbA1c)  $\geq$  8% (patients can be rescreened after diabetes is brought under adequate control, or in case HbA1c < 8%).
12. Known defects in visual fields due to optic chiasmal compression or other neurological signs, related to the pituitary tumor mass. Patients with long-standing (>12 months), fixed, minor defects may be considered on a case-by-case basis after consultation with the medical monitor.
13. Female patients who are pregnant or lactating or intending to become pregnant during the study.
14. Known history of immunodeficiency (e.g., HIV positive).

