### 5.8.6 Abdominal Ultrasound

Abdominal ultrasound will be conducted to monitor gall bladder and biliary tract disease as specified in Schedule of Assessments ([Appendix A](#)). Abdominal ultrasound may be repeated during the treatment period to comply with local guidelines. Evidence of cholelithiasis, biliary sludge, and bile duct dilatation will be documented.

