### **Liver Dysfunction**

Somatostatin analogs including octreotide have been associated with liver function abnormalities, as well as sporadic post-marketing reports of acute hepatitis with or without cholestasis, jaundice and cholestatic jaundice.

Octreotide inhibits secretion of cholecystokinin, resulting in reduced contractility of the gallbladder and an increased risk of sludge and stone formation. Biliary disease is the most common reasons for liver dysfunction in acromegaly patients.

Liver function tests (ALT, AST and Bilirubin), will be monitored routinely at all scheduled visits during all periods of the study. Liver function tests could also be assessed at any unscheduled study visit, as clinically indicated.

Patients who develop liver function abnormalities (elevated transaminases to  $>3 \times \text{ULN}$ ) during the study should be evaluated for common causes of hepatitis such as cholestasis, alcoholic liver disease, non-alcoholic steatohepatitis, environmental exposures, other drug/herbal supplement exposures, viral or autoimmune hepatitis. The diagnostic work up of liver dysfunction should be guided by the patient's medical history and physical exam, and local practice, at the investigator discretion.

Patients with asymptomatic liver dysfunction (i.e., ALT or AST  $>3 \times \text{ULN}$  and  $< 5 \times \text{ULN}$  and total bilirubin  $< 2 \times \text{ULN}$ ), may continue to receive study drug (Figure 2). Liver function tests must be repeated in 7 days. In case of continued transaminase elevation, periodical follow up visits should be considered, per the investigator discretion up to resolution/return to baseline. Follow up should include monitoring of symptoms potentially associated with acute hepatitis (new appearance of fatigue, nausea, vomiting, right upper quadrant pain or tenderness, fever, rash, and/or eosinophilia), or with complications of cholestasis (e.g. cholangitis). In case of symptoms suggestive of cholestasis, a follow up abdominal ultrasound should be considered. Local assessment of INR could be added to the liver function tests, based on the investigator discretion.

[figure not shown]

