#### **8.4.8.4 ECG, Ultrasound**

All 12-Lead ECGs will be read by a central lab. 12-Lead ECG parameters will be summarized at each time point using descriptive statistics by final dose group and treatment group (i.e., octreotide 40, 60, 80, overall and placebo). Both absolute and change from baseline will be provided for each continuous 12-Lead ECG parameter. Summaries will be provided for the DPC period and for the OLE period. In calculating the change from baseline for both the DPC and for the OLE, the baseline for the DPC period will be used. Additionally, the numbers and percentages of patients with ECG abnormalities (as determined by the central laboratory) at each visit will be presented for both the DPC and for the OLE.

Shift tables will be used to show the changes from baseline to each post baseline time point based on pre-defined abnormality criteria for both the DPC and for the OLE periods. For both the DPC period and the OLE period, shifts from baseline will use the baseline defined for the start of the DPC period.

The following information will be summarized at baseline and end of treatment for the DPC period using shift tables, by final dose group and treatment group:

- Ultrasound Normality (Normal=Yes reported on eCRF; Abnormal = No)
- Biliary Sludge (Normal=No reported on eCRF; Abnormal =Yes)
- Wall Thickening (Normal=No reported on eCRF; Abnormal =Yes)
- Dilatation of Common Bile Duct (Normal=No reported on eCRF; Abnormal =Yes)

For the OLE period, shift tables will also be provided to show shifts from baseline of the DPC period to each assessment in the OLE period.

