## 5.2 Safety Endpoints

1. Incidence of adverse events (AEs)
2. Incidence of adverse events of special interest (AESI) overall and by AESI.
3. Absolute and change from baseline to each study visit in blood chemistry parameters
4. Absolute and change from baseline to each study visit in blood hematology parameters
5. Absolute and change from baseline to each study visit for Vital Signs (HR, SBP, DBP, Body Weight) and 12-lead ECG (PR, QRS, QTcF, HR)
6. Incidence of clinically significant findings on abdominal ultrasound

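### The ultrasound shift tables have no gallstone row, and the ultrasound safety endpoint has no specified table or listing, so stones are reported by name only if recorded as adverse events

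*SAP*

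**What the plan says.** Protocol 7.6 (Liver Dysfunction) describes the effect of octreotide on the gallbladder as "resulting in reduced contractility of the gallbladder and an increased risk of sludge and stone formation". Protocol 5.8.6 sets out what the scans must capture: "Evidence of cholelithiasis, biliary sludge, and bile duct dilatation will be documented".

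The analysis list is the same in SAP 6.9.6 and protocol 8.4.8.4. It has four items, each a baseline to end-of-treatment shift table. The first is whether the scan as a whole was read as normal. The second is sludge, entered as "Biliary Sludge (Normal=No reported on eCRF; Abnormal =Yes". The other two, coded in the same yes/no way, are a thickened wall and a dilated common bile duct.

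For the open-label extension, SAP 6.9.6 adds shift tables from the double-blind baseline to each extension assessment. Neither list carries a redaction mark.

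SAP 5.2 lists as its sixth safety endpoint "Incidence of clinically significant findings on abdominal ultrasound"; protocol 2.2.2 has the same item. At entry, protocol 4.2 excludes only "Symptomatic cholelithiasis", and protocol 4.1 requires at least 6 months of prior injectable SRL treatment.

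**The concern.** The protocol names two biliary risks, sludge and stones, and asks for both to be documented. Only sludge is carried into the analysis as a finding of its own. Wall thickening, which 5.8.6 does not mention, has a row.

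The only existing row that a stone can move by itself is overall normality. That row is binary, so it cannot register a second abnormality in a patient whose first scan was already abnormal. Such patients can enter, because asymptomatic stones, sludge and other silent findings are not excluded.

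At stake is what the study report can say about gallstones from scheduled imaging. These scans exist to find silent disease, which symptom-driven reporting is least likely to pick up. The extension tables use the same baseline, so the gap continues through long-term exposure.

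**Working it through.** The plan gives no figure to reproduce. The check compares the passages and then follows a new stone through the tables.

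**Step 1. Findings against rows.**

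| Finding | Named as an octreotide risk (protocol 7.6) | To be documented (protocol 5.8.6) | Own shift row (SAP 6.9.6, protocol 8.4.8.4) |
|---|---|---|---|
| Gallstones | Yes | Yes | No |
| Sludge | Yes | Yes | Yes |
| Bile duct dilatation | No | Yes | Yes |
| Wall thickening | No | No | Yes |

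Two of the three findings that must be documented have a row. Gallstones do not.

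**Step 2. A new isolated stone**, meaning one without new sludge, wall thickening or duct dilatation.

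| Baseline scan | Normality row | Other three rows | What the tables show | A cholelithiasis row would show |
|---|---|---|---|---|
| Normal | Normal to abnormal | No change | An unspecified abnormality | No to Yes |
| Abnormal, no stones | Abnormal to abnormal | No change | Nothing | No to Yes |
| Abnormal, stones present | Abnormal to abnormal | No change | Nothing | Yes to Yes (still nothing) |

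**Step 3. Output for the sixth safety endpoint.** None of the four rows records clinical significance, so none gives the stated incidence. SAP 6.9.3, 6.9.4 and 6.9.5 each provide a listing of clinically significant abnormalities, for laboratory values, vital signs and ECG. SAP 6.9.6 does not. Its one listing sentence concerns data collected after study drug was stopped.

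**Step 4. The adverse event route.** Protocol 7.1 treats a new condition as an adverse event. It treats an abnormal diagnostic result as one if it leads to withdrawal, comes with signs or symptoms, changes study or concomitant medication, or is judged clinically significant. SAP 6.9.2.1 and 6.9.2.2 tabulate treatment-emergent events down to preferred term. This route has two limits:

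- A silent stone enters only if the investigator records it as an event.
- For the double-blind period, SAP 6.9.2.1 closes the window at the last dose of blinded drug, and SAP 6.9 and 6.9.6 drop later data from the tables. Under protocol 5.4, a patient who stops early has a scan at the end-of-treatment visit, which may be scheduled separately. If that visit follows the last dose, a stone first seen there can, read literally, miss both the shift tables and the double-blind event tables.

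**Step 5. Scale.** About 50 patients randomised 1:1 gives 50 / 2 = 25 per arm. One patient is 1 / 25 = 4 percentage points. The documents give neither the share of abnormal baseline scans nor a rate of new stones, so an expected number missed cannot be calculated.

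**The case against.** The strongest reply is that the plan does not rest on the shift tables alone. A stone recorded as an adverse event appears under its own preferred term, by treatment group, whatever the baseline scan showed. The sixth safety endpoint is limited to clinically significant findings, and the investigator's judgement of clinical significance is itself a trigger for recording an adverse event, so the event tables should carry much of the same information. For patients who complete on drug, the schedule places the scan and on-site dosing at the same Week 36 visit, so the window problem falls mainly on early discontinuers. These are also descriptive tables with no hypothesis test.

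Much of this stands. A reader might infer that new stones leave no trace, or that the trial cannot report them. The documents do not support either reading, because the adverse event route exists. Nor do they rank stones above sludge, since 7.6 names the two together, and they do not show that patients with abnormal baselines are the most prone to new stones.

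The reply does not close the gap. It makes the reporting of a named imaging finding depend on whether each investigator enters a silent result as an event, when the protocol already requires that finding to be documented. It also leaves a listed endpoint without a defined output.

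**Conclusion.** The concern holds as a reporting gap in the safety analysis. The ultrasound tables cannot show a new isolated stone when the baseline scan was abnormal, and cannot identify it as a stone when the baseline was normal. Outside those tables, stones are tabulated only when recorded as adverse events within the window. The sixth safety endpoint has no specified table or listing.

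The gap follows from the wording of the two lists and needs no assumption about prevalence. The number of patients affected is unknown. The primary and secondary efficacy analyses are not affected. The change is worth making before the tables are produced, because it alters what the report can say about a risk that the protocol itself names.

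**What to change.** 1. Add a row, Cholelithiasis (Normal = No; Abnormal = Yes), to the lists in SAP 6.9.6 and protocol 8.4.8.4, for the double-blind and open-label periods.
2. First confirm that the eCRF holds a cholelithiasis field. The existing rows are tied to eCRF entries, and protocol 5.8.6 requires the finding to be documented without saying that it is a separate coded item. If there is no field, derive the variable from the documented scan findings.
3. Add one table, by treatment group, of patients with a clinically significant ultrasound finding that was not present at baseline, so that the sixth safety endpoint has an output.

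The cost is two small descriptive tables and possibly one derived variable. The cholelithiasis row has a limit that should be stated with it: a patient with stones at baseline will read Yes to Yes, so additional stones in that patient will still not appear.
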